6.5. Dose Modification

Dose modifications of lebrikizumab are not allowed in this study.

6.6. Continued Access to Study Intervention after the End of the Study

Lebrikizumab will be made available to eligible participants who complete Visit 9 (Week 24) via the Continued Access addendum, until lebrikizumab is commercially available in the US. Please refer to KGBO Protocol Addendum 2 for additional information. Otherwise, lebrikizumab will not be provided after participants exit this study.

6.7. Treatment of Overdose

For this study, any dose of lebrikizumab greater than 500 mg (baseline and Week 2) and 250 mg Q2W (Week 4 and beyond) will be considered an overdose.

Sponsor does not recommend specific treatment for an overdose.

In the event of an overdose, the investigator/treating physician should:

- Contact the medical monitor immediately.
- Evaluate the participant to determine, in consultation with the medical monitor, whether study intervention should be interrupted or whether the dose should be reduced.
- Closely monitor the participant for any AE/SAE and laboratory abnormalities until lebrikizumab can no longer be detected systemically (at least 18 weeks).

6.8. Concomitant Therapy

Any medication or vaccine (including over-the-counter or prescription medicines, vitamins, antacids, and/or herbal supplements) that the participant is receiving at the time of enrollment or receives during the study must be recorded along with:

- reason for use
- dates of administration including start and end dates
- dosage information including dose and frequency for concomitant therapy of special interest

The medical monitor should be contacted prior to entering the participant into the study if there are any questions regarding concomitant or prior therapy.

Participants should be instructed to consult with the investigator prior to initiating any new medication (either self-administered non-prescription drugs or prescription therapy prescribed by another physician) while participating in the study. The investigator is expected to examine the acceptability of all concomitant medications, topical preparations, and dietary supplements taken by participants in the study.

The use of any concomitant medication must relate to an AE listed on the AE case report form (CRF) or the participant's medical history, unless the medication is a supplement or used as preventive care.

6.8.1. Permitted Treatments and Procedures

The following therapies will **be permitted** during the study:

Permitted Concomitant Medications and Vaccines	Comments
Medications	
Medications for medical conditions other than AD (for example, hypertension or diabetes)	
Low and /or mid potency TCS, TCIs (for example, tacrolimus and pimecrolimus), or topical PDE-4	Permitted as needed on AD lesions and must be documented in the diary

Permitted Concomitant Medications and Vaccines	Comments
inhibitors (for example, crisaborole) for treatment of AD (see Section 6.8.4)	
High-potency TCS for treatment of AD	Permitted up to 10 days
Non-medicated moisturizers	
Intranasal corticosteroids	
Inhaled corticosteroids and bronchodilators to control asthma	
Single intra-articular (bursa, tendons, and ligaments) corticosteroid injection	
Non-sedating antihistamines	
Ophthalmic drugs containing antihistamines, corticosteroids, or other immunosuppressants	
Allergen immunotherapies	If on maintenance dose
Leukotriene inhibitors	
Acute Systemic and topical anti-infectives/antibiotics	For treatment of acute infections
Sedating systemic antihistamines including, but not limited to, alimemazine, chlorphenamine, clemastine, cyproheptadine, diphenhydramine, hydroxyzine, ketotifen, and promethazine	On an as needed basis
Systemic/oral sleep aid medications	On an as needed basis
Recreational use of cannabis and cannabinoid (if allowed per local regulations/law)	Not allowed for the treatment of pruritus, pain and/or AD
Vaccines	
Non-live vaccinations	Including non-live SARS-CoV-2 vaccines, RNA vaccines, vaccines with inactive viral elements, and/or non-replicating viral vectors that are clinically indicated

Abbreviations: AD = atopic dermatitis; RNA = Ribonucleic acid; SARS-CoV-2 = severe acute respiratory syndrome coronavirus 2; PDE-4 = phosphodiesterase-4; TCI = topical calcineurin inhibitors; TCS = topical corticosteroids.

NOTE: In the context of this table, “during the study” = from screening to post-treatment safety follow-up visit.

6.8.2. Prohibited Treatments and Procedures

The following therapies will be prohibited during the study:

Prohibited Concomitant Medications, Vaccinations, and Procedures	Comments
Medications or procedures	
Systemic corticosteroids (IM, PO, or IV)	NOTE: Any use of systemic corticosteroids will be considered as rescue medication (see Section 6.8.5)
Any investigational drug other than the study drug	
B cell-depleting biologics, including rituximab	
Other biologic agents (other than the study interventions)	
Topical JAK inhibitor for treatment of AD	Any use will be considered as rescue medication (see Section 6.8.5)

Prohibited Concomitant Medications, Vaccinations, and Procedures	Comments
TCS (high potency)	Use for >10 days is prohibited
Medications or therapies for other medical conditions known to affect AD (for example, immunosuppressive/immunomodulating drugs such as systemic corticosteroids, mycophenolate mofetil, IFN-gamma, topical, and systemic JAK inhibitors, cyclosporine, azathioprine, or methotrexate; phototherapy or PUVA; or systemic PDE-4 inhibitors)	
Chronic Systemic and topical anti-infectives	For chronic treatment during the study
Planned or anticipated major medical procedures or surgeries	
Tanning booth/parlor	
Bleach bath	
Use of cannabis or cannabinoids for the treatment of pruritus, pain and/or AD	
Vaccines	
Live or live attenuated vaccines, as well as BCG vaccine	

Abbreviations: AD = atopic dermatitis; AE = adverse event; BCG = Bacillus Calmette-Guerin; JAK = Janus kinase; IFN = interferon; IM = intramuscular; IV = intravenous; PDE-4 = phosphodiesterase-4; PUVA = photochemotherapy; TCS = topical corticosteroids; PO = by mouth.

NOTE: in the context of this table, “during the study” = from screening to post-treatment safety follow-up visit.

6.8.3. Non-Medicated Moisturizers

Participants may apply a stable dose of non-medicated topical moisturizer at least twice daily for ≥ 7 days prior to the baseline visit and throughout the study.

The participants may continue their current over-the-counter moisturizer regimen, if approved by the investigator.

All moisturizer use should be recorded in the CRF.

6.8.4. Topical Treatment for Atopic Dermatitis

The goal of this Phase 3b study is to demonstrate the safety and efficacy of lebrikizumab for moderate-to-severe AD in a population previously treated with dupilumab. Regular use of non-medicated, non-prescription moisturizers should be used by all participants. During this study, topical therapies may be needed if the participant experiences intolerable clinical worsening of symptoms. If needed, investigators are encouraged to recommend therapy in a staged fashion, beginning with a topical low-potency treatment first, then topical mid-potency treatment if needed. In sensitive skin areas (that is, face, neck, intertriginous, and genital areas), only low-potency topical treatments should be used.

If AD lesions recur or a participant experiences a flare, as needed use of low- and/or mid-potency TCS, TCI (tacrolimus or pimecrolimus), and/or topical PDE4 inhibitors (crisaborole) may be initiated at the participant’s discretion but must be communicated to the investigator and documented in the patient diary or as concomitant medications.

Escalation to high-potency topical corticosteroid medications should only occur if participants do not respond adequately after at least 7 days of low/mid potency TCS, TCI and/or topical PDE4 inhibitors. Use of high-potency TCS for more than 10 days is considered rescue therapy (Section 6.8.5). Participants that receive Rescue therapy must be discontinued from the study. (see Section 7.1). All topical therapy usage must be recorded in the CRF or patient diary.

6.8.5. Rescue Medicine for Atopic Dermatitis

To be consistent with real world practice, defined topical medications are allowed in this study (see Section 6.8.4). However, rescue therapies may be needed if the participant experiences intolerable clinical worsening of symptoms. Escalation to high potency topical TCS, topical JAK inhibitors, phototherapy and/or systemic medications (including but not limited to corticosteroids, immunosuppressants, biologics, small molecules, etc.) for the treatment of AD should only occur if participants do not respond adequately after at least 7 days of low/mid potency TCS, TCI and/or topical PDE4 inhibitors. Any use of topical JAKs, phototherapy, and/or systemic medications will be considered rescue therapy. Use of high-potency TCS for more than 10 days is also considered rescue therapy. Participants that receive Rescue therapy must be discontinued from the study. (see Section 7.1).

All rescue medication must be recorded in the CRF.

7. Discontinuation of Study Intervention and Participant Discontinuation/Withdrawal

Discontinuation of specific sites or of the study as a whole are handled as part of Appendix 1.

7.1. Discontinuation of Study Intervention

When necessary, a participant may be permanently discontinued from study intervention. If so, the participant will remain in the study to complete procedures for an early discontinuation visit and post-treatment follow-up, if applicable, as shown in the SoA.

A participant should be permanently discontinued from study intervention if

- the participant becomes pregnant during the study
- in the opinion of the investigator, the participant should permanently discontinue the study intervention for safety reasons
- the participant develops a malignancy, except for successfully treated basal or squamous cell skin carcinoma
- the participant tests positive for HBV DNA (see Section 8.2.3)
- the participant tests positive for HCV RNA (Section 8.2.4)
- if the participant experiences a hepatic event or liver test abnormality as specified in the liver chemistry stopping criteria (see Section 7.1.1)
- the participant develops HIV infection
- the participant requires rescue medication treatment for symptoms of AD in the treatment period
- the participant develops any infection that is opportunistic, such as active tuberculosis and other infections whose nature or course may suggest an immuno-compromised status, and
- the participant has an AE or an SAE or a clinically significant change in a laboratory value that, in the opinion of the investigator, merits discontinuation of study intervention and appropriate measures being taken.

Hepatitis

- prior to discontinuation of any immunomodulatory and/or immunosuppressive therapy due to hepatitis, including study intervention, the participant is to be referred to, evaluated, and managed by a specialist physician with expertise in evaluation and management of viral hepatitis.
- the timing of discontinuation from study intervention relative to the initiation of any antiviral treatment for hepatitis is to be based on the recommendation of the consulting specialist physician, in conjunction with the investigator, and aligned with medical guidelines and standard of care.

Hypersensitivity

- if the investigator determines that a systemic hypersensitivity reaction has occurred related to study intervention administration, the participant may be permanently discontinued from the study intervention, and the sponsor's designated medical monitor

should be notified. If the investigator is uncertain about whether a systemic hypersensitivity reaction has occurred and whether discontinuation of study intervention is warranted, the investigator may consult the sponsor.

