7.1.1. Liver Chemistry Stopping Criteria

The study drug should be interrupted and close hepatic monitoring initiated (see Section 8.2.2) if 1 or more of these conditions occur:

Elevation ^a	Exception ^a
ALT or AST >8x ULN	
ALT or AST >5x ULN for more than 2 weeks	
ALT or AST >3x ULN and either TBL >2x ULN or INR >1.5	For participants with Gilbert's syndrome: If baseline direct bilirubin is >0.5 mg/dL, then doubling of direct bilirubin should be used for drug interruption decisions rather than TBL >2x ULN.
ALT or AST >3x ULN with the appearance of fatigue, nausea, vomiting, right upper quadrant pain or tenderness, fever, and/or rash	
ALP >3x ULN, when the source of increased ALP is the liver	
ALP >2.5x ULN and TBL > 2x ULN	For participants with Gilbert's syndrome: If baseline direct bilirubin is >0.5 mg/dL, then doubling of direct bilirubin should be used for drug interruption decisions rather than TBL >2x ULN.
ALP >2.5x ULN with the appearance of fatigue, nausea, vomiting, right upper quadrant pain or tenderness, fever, and rash	
Source: FDA Guidance for Industry: Drug-Induced Liver Injury: Premarketing Clinical Evaluation, July 2009 and other consensus guidelines, with minor modifications.	

Abbreviations: ALP = alkaline phosphatase; ALT = alanine aminotransferase; AST = aspartate aminotransferase; INR = international normalized ratio; TBL = total bilirubin; ULN = upper limit of normal.

^a All ULN values should be age adjusted (AAULN) for participants <18 years of age.

Resumption of the study intervention can be considered only in consultation with the Lilly-designated medical monitor and only if liver test results return to baseline and if a self-limiting non-drug etiology is identified. Otherwise, study intervention should be discontinued.

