7.1.2. Temporary Discontinuation of Study Intervention

Temporary withholding of study intervention is required if the participant meets any of the following infection-related criteria during the study:

- Serious or opportunistic infections, as defined in Section 5.2. Study intervention is to be withheld until resolution of all acute clinical signs and symptoms, and completion of all appropriate anti-infective treatment.
- HBV DNA results that are reported as positive, or as detecting HBV DNA, but HBV DNA is below the level of quantification. In this situation, the sponsor's designated medical monitor should be contacted regarding the participant's status. HBV DNA testing is to be repeated as soon as is feasible. If HBV DNA is confirmed as positive, the participant must be permanently discontinued from study intervention as described in Section 7.1.
- If a participant <18 years of age loses a clinically significant amount of weight (below 40 kg), the investigator should assess rationale for weight loss and use clinical judgment to determine if the participant should temporarily discontinue the treatment.

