## 5.2.1. Primary Estimand for the Primary Endpoint

The primary estimand for the primary endpoint represents the primary clinical question of interest: What is the intervention effect in percentage of participants achieving at least 75% improvement from baseline in Eczema Area and Severity Index (EASI) after 16 weeks of lebrikizumab 250 mg Q2W intervention in participants with moderate-to-severe AD who have been previously treated with dupilumab and who remain on study treatment until Week 16?

The primary estimand for the primary endpoint is described by the following attributes:

- A. Population: participants with moderate-to-severe AD who have been previously treated with dupilumab and who remain on study treatment until Week 16.
- B. Endpoint: whether participants achieve at least 75% improvement from baseline in EASI at Week 16.

- C. Intercurrent events: There are no intercurrent events for this population since participants who initiate rescue medication are discontinued from the study and hence study treatment. Therefore, participants who stay on study treatment through Week 16 will not have an intercurrent event such as initiating rescue medication or permanently discontinuing treatment.
- D. Population-level summary: percentage of participants achieving EASI-75 response at Week 16.

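### Protocol 7.1 and 7.1.1 give incompatible instructions on re-exposure after a liver stopping criterion is met, for events that satisfy all three resumption conditions

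*Protocol*

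**What the plan says.** Protocol 7.1 introduces its list with "A participant should be permanently discontinued from study intervention if". One bullet in that list reads "if the participant experiences a hepatic event or liver test abnormality as specified in the liver chemistry stopping criteria (see Section 7.1.1". The bullet has no exception and does not mention resumption.

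Protocol 7.1.1 opens its table of liver values with a different instruction: "The study drug should be interrupted and close hepatic monitoring initiated (see Section 8.2.2) if 1 or more of these conditions occur". Below the table it says "Resumption of the study intervention can be considered only in consultation with the Lilly-designated medical monitor", and then adds "only if liver test results return to baseline and if a self-limiting non-drug etiology is identified". It closes with "Otherwise, study intervention should be discontinued".

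Protocol 7.1.2, the section on temporary discontinuation, begins "Temporary withholding of study intervention is required if the participant meets any of the following infection-related criteria during the study". It covers serious or opportunistic infection, low-level HBV DNA and weight loss in adolescents. It lists no liver chemistry criterion.

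On the analysis side, SAP 5.2.1 restricts the primary estimand to participants "who remain on study treatment until Week 16". SAP 5.2.2 and 5.2.4 name permanent treatment discontinuation as the only intercurrent event of the supportive estimands.

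**The concern.** The two sections share one set of triggers but state different consequences. Section 7.1 refers to 7.1.1 to identify which abnormalities count, and its own lead-in already fixes what follows from them. An investigator who reads 7.1 alone stops the drug for good and has no reason to raise resumption with the medical monitor. An investigator who reads 7.1.1 interrupts, investigates and may raise it. Both can claim to be following the protocol.

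What is at stake is whether a participant who has had, for example, ALT above 8 times the upper limit of normal may be given the drug again. There is also a smaller effect on data collection. Protocol 8.2.2 asks for the hepatic safety form when study drug is discontinued because of a hepatic event, while its ALT trigger needs two consecutive raised tests. A single high ALT that falls below that trigger on repeat, with no other trigger met, would call for the form if treatment were stopped. On the natural reading it would not if treatment were interrupted and resumed.

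**Working it through.** The plan states no figure on this point, so the check is a comparison of text. Dosing stops at once under either section. The question is what may follow.

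| Situation after a 7.1.1 criterion is met | Outcome under 7.1 | Outcome under 7.1.1 | Do they agree? |
|---|---|---|---|
| Liver tests do not return to baseline | Treatment ends | Treatment ends | Yes |
| No self-limiting non-drug cause is identified | Treatment ends | Treatment ends | Yes |
| Both of these are satisfied, but the medical monitor is not consulted | Treatment ends | Resumption is not open; treatment ends | Yes |
| All three conditions hold | Treatment ends permanently | Resumption may be considered | No |

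The conflict is confined to the last row. Even there, 7.1.1 permits resumption and does not require it.

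Next, does any other text settle the last row? Neither section states precedence. Elsewhere the protocol writes out its qualifications:

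- The malignancy bullet in 7.1 carries its own exception, for successfully treated basal or squamous cell skin carcinoma.
- Low-level HBV DNA has an explicit staged rule in 7.1.2: withhold, repeat the test, and stop permanently under 7.1 if it is confirmed. Section 8.2.3 points to both outcomes.

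The liver chemistry bullet has no such exception or link, and 7.1.2 does not supply one.

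Finally, the size of any effect on the primary result:

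- Inputs: 120 participants and an anticipated EASI-75 rate of about 50% (Protocol 9.5, SAP 4.2), so 0.50 × 120 = 60 responders. The planned 90% interval at 50% is 42.6% to 57.4%.
- All participants retained: 60/120 = 50.0%.
- One responder leaves the Week 16 set: 59/119 = 49.6%, a change of 0.4 points.
- One non-responder leaves: 60/119 = 50.4%, a change of 0.4 points the other way, through the denominator only.
- Half-width of the planned interval: (57.4 − 42.6)/2 = 7.4 points.

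One such participant therefore moves the estimate by about 0.4/7.4, or 5%, of the half-width.

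**The case against.** The strongest reply is that the sections can be read together. Section 7.1.1 is a subsection of 7.1, the bullet refers to it, and it sets out a sequence in which discontinuation is the default unless every condition for resumption is met. On that reading the bullet is shorthand for the end of the pathway. This is a reasonable reading, but the text does not establish it. The lead-in to 7.1 says permanent without qualification, and the authors wrote exceptions and staged links where they wanted them.

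The rest of the reply limits the point, and it stands:

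- A reader might infer that a site could choose to re-dose on its own. It could not, because 7.1.1 makes consultation with the medical monitor a condition.
- A reader might infer that a given liver value by itself opens opposite instructions. It does not. Divergence needs recovery to baseline and an identified non-drug cause as well.
- Different outcomes for similar events would not vanish if the wording were aligned to the 7.1.1 pathway. Section 7.1 separately lets the investigator stop treatment permanently for safety reasons, and resumption under 7.1.1 is only permissive.
- A reader might infer that the analysis is left undefined. Largely it is not. SAP 5.2.1 describes the relevant event as permanent discontinuation, so an interruption is not an intercurrent event. The discontinuation tables in SAP 5.7 and 5.13.2.2 count what actually happened.

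**Conclusion.** The contradiction is real and narrow. For liver events that meet all three resumption conditions, Protocol 7.1 forbids re-exposure and 7.1.1 allows it to be considered. For every other liver event the two agree that treatment ends. It is an inconsistency within a safety rule and cannot be defended as a choice of design.

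It might be tempting to argue that the conflict threatens the primary result. The documents do not support that. The effect is about 0.4 points per participant, the study is descriptive, and no hypothesis test or decision criterion depends on the estimate. That arithmetic assumes 60 responders among 120 and one affected participant whose Week 16 value is lost. The documents give no rate for liver criteria events, so the number of participants affected cannot be estimated. The reason to correct the text is that a hepatic stopping rule should give one instruction before an event occurs, however few events there are.

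**What to change.** Reconcile the liver bullet in Protocol 7.1 with 7.1.1 so that one rule applies once a liver criterion is met, and make 7.1.2 consistent with whatever is decided. The sponsor's clinical team must choose the rule, and this review does not say which one is right.

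Optionally, if interruption followed by resumption remains possible, add a sentence to SAP 5.2.1 saying whether such a participant counts as having remained on study treatment until Week 16. The SAP's focus on permanent discontinuation already points to an answer, so this is a clarification only.

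The cost is about a sentence of protocol text in the next amendment and, if wanted, one sentence in the SAP. No procedure, visit or analysis is added.
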